This prospective randomised controlled trial will recruit healthy adult volunteers from a university population to participate. To avoid the involvement of individuals with unequal relationships, participants will be recruited through the form of advertisements on staff and student noticeboards, and through an email invitation sent to students within the faculty. A power analysis demonstrated that a total of 30 participants would be required to achieve a power of 0.8 and alpha error probability of 0.05 for a small-medium effect size of $f=0.2$. Each participant will take part in every condition to eliminate the risk of demographic factors confounding the results. Each of the 5 devices being investigated will comprise each of the test conditions. The order in which participants complete the 5 test conditions will be randomised in advance using a computer random number generator. Testing will involve each device being applied and used according to the manufacturers' instructions. Where a device has the ability to apply different temperatures and pressures to participants, settings will be selected in accordance with manufacturer guidelines and recommendations for use. Each testing session will take around 60 minutes to complete, depending on the treatment application guidelines of each device, with at least 24 hours between tests involving the same participant. In total, participants will be giving around 5 hours of time across 5 days to complete their participation.

Inclusion and exclusion criteria

Participants ≥ 18 years old will be considered eligible for the study unless they meet any of the following exclusion criteria, which include the common contraindications for cold therapy (Selfe *et al.*, 2009; Fang *et al.*, 2012; Waterman *et al.*, 2012):

- BMI >40 kg/m²
- History of nerve damage or sensory deficit in the lower limbs (including frostbite)
- Hypersensitivity to cold, including hives
- Active inflammation or pain of the knee
- History of thrombosis, embolism, or other conditions related to impaired peripheral circulation
- Suffering from diagnosed diabetes, multiple sclerosis, rheumatoid arthritis, spinal cord injury, cardiovascular disease, hypertension, Raynaud disease, cryoglobulinemia, or haemoglobinuria
- Confirmed or suspected tissue infection, an unstable fracture, a skin condition, or a tumour in the treatment area
- Cognitive impairment or communication barriers where adjustments can not be reasonably made

Protocol

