Upon completion of a test, the cuff will be removed. If the temperature of the skin has been reduced to within 10-15°C, skin temperature will continue to be monitored every 5 minutes after the cuff has been removed until it rises above 15°C, at which point the test will end. This will allow for the total time to be measured that skin temperature remains within the target therapeutic range as a result of a single application of the cryocompression device. If the skin temperature is not reduced to within 10-15°C while the cuff is worn, then the test will end after the cuff is initially removed. Upon completion of the test, the temperature sensor will be removed from the leg of the participant; thus completing their participation in the test. Once each participant has taken part in all conditions, they will have completed their participation in the study.

The following measures will be recorded: skin temperature at each time point, minimum skin temperature achieved, time to achieve minimum skin temperature, length of time with skin temperature within therapeutic range of 10-15°C. After each test, participants will also be asked to respond to the following question using a 5-point Likert scale: "How comfortable did you find the treatment you just experienced?" The possible answers to this question will be: "Very comfortable, Comfortable, Neutral, Uncomfortable, Very uncomfortable". This will provide insight into differences in perception of the treatment, which could be relevant for the likelihood of protocol adherence by patients in clinical settings.

Analysis

The data will be analysed to detect any differences during testing compared to baseline measures, and between groups. All data will be first subjected to a Kolmogorov-Smirnov test to assess whether they are normally distributed. A repeated measures analysis of variance will be performed on all normally distributed data. A Friedman test will be performed on any data that are not normally distributed.

Ethical issues

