There is a low risk of cold injury to participants if their skin temperature is reduced to <10°C for any prolonged period of time (>60 mins). The coldest temperature setting for this study is 1°C (GameReady), which will be applied for 30 mins. A recent study conducted at the University of Winchester demonstrated that device temperature settings do not equal the actual skin temperatures achieved, and it is not expected that skin temperatures will be reduced to lower than 6°C for more than 15 minutes during any test. Therefore, the risk of harm to the participant is deemed to be minimal for this study.

Participants have the right to withdraw themselves and any collected data from the study at any time during, and for the first 7 days after, their participation without having to give a reason. They also have the right to terminate a test session at any time. Testing shall also be terminated as a result of any adverse reactions that emerge. Adverse reactions (e.g. pain) to the testing protocol are not expected due to the low-risk nature of the study, however any that occur shall be recorded and monitored until things return to baseline/normal. In

order to monitor any pain/discomfort that might occur, a Numerical Pain Rating Scale (0-10 scale) will be within sight of the participant at all times during testing: a test will be terminated if reported pain/discomfort exceeds 5/10, though none is expected. Any reported pain (or other adverse reactions) shall be stored along with the data collected for that participant. If a test is terminated for a reason that could be mitigated in future, participants will be offered the opportunity to repeat the test another day, should they wish to continue taking part in the study. If a test is terminated due to an adverse reaction that can not be mitigated in future, the participant (and any collected data) will be thanked for their time and withdrawn from the study.

Conflict of interest declaration

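### A session that is missed, or ended and not repeated, removes the participant's other valid sessions from the planned complete-block tests, and the sample of 30 has no allowance for this

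*Combined protocol and SAP*

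**What the plan says.** **Tests.** The Analysis section specifies "A repeated measures analysis of variance will be performed on all normally distributed data. A Friedman test will be performed on any data that are" (non-normal data). It names no other model, analysis set, imputation or rule for missing sessions.

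**Sample size.** The Design section states that "a total of 30 participants would be required to achieve a power of 0.8 and alpha error probability of 0.05", for an effect size f of 0.2. It mentions no allowance for incomplete sets and no replacement of participants. The comparison is wholly within person: "Each participant will take part in every condition to eliminate the risk of demographic factors confounding the results". There are five devices, on five days at least 24 hours apart.

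**Ways to an incomplete set.** The Ethical issues section says "Participants have the right to withdraw themselves and any collected data from the study at any time during, and for the first 7 days after" (that is, after taking part). Removal of data is thus a right that the participant may or may not use. Participants may also end any session, and pain above 5/10 ends a test. A repeat is offered when the cause can be mitigated and the participant wishes to go on. After an adverse reaction that cannot be mitigated, the participant and the collected data are withdrawn. Nothing is said about a session that is missed, or ended and not repeated, when the data stay in.

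**Readings.** The Protocol section records skin temperature at baseline and every 5 minutes during the 30-minute test, so a session ended early still holds some values.

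**The concern.** Repeated-measures ANOVA and the Friedman test, in their usual form, work on complete blocks. A participant who attends four visits and misses the fifth leaves four valid sessions that neither test can use. Two things are then at stake.

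- **Power.** Each incomplete participant costs a whole block, not one session out of five. If 30 is the number required, any such loss takes the study below its target.
- **Prespecification.** With no rule in the plan, someone must decide how to treat incomplete sets after the data are in. The Conflict of interest declaration says that the lead is paid by the maker of compared devices, which is a further reason to fix the rule in advance.

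**Working it through.** **Inputs.** From the Design section: n = 30, power 0.8, alpha 0.05, f = 0.2, m = 5 devices. Not stated, so assumed: the correlation between conditions (rho), the sphericity factor (epsilon) and the share of sessions missing.

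**1. The plan's own figure.** For a one-group within-participant F test,

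lambda = f² × n × m × epsilon / (1 − rho), df1 = (m − 1) × epsilon, df2 = (n − 1)(m − 1) × epsilon.

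With rho = 0.5 and epsilon = 1, lambda = 0.04 × 30 × 5 / 0.5 = 12.0 on 4 and 116 df. Power is 0.784, and 32 participants are needed to exceed 0.80. The stated 30 is therefore reproduced to within 2 participants, with no slack. At rho = 0.4 the requirement is 38 and at rho = 0.6 it is 26 (epsilon = 1 in both). At rho = 0.5 with epsilon = 0.75 it is 38.

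**2. Calibration to the stated power.** To give the plan exactly its 0.80 at 30 complete sets, take lambda = 12.43 and scale it by n/30.

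**3. Complete-set analysis.** If each session is missing independently with probability p:

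- complete sets = 30 × (1 − p)^5
- valid sessions = 150 × (1 − p)
- valid sessions discarded = valid sessions − 5 × complete sets

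| Sessions missing (assumed) | Complete sets | Valid sessions discarded | Power, complete sets | Power, all available sessions |
|---|---|---|---|---|
| 1% | 28.5 | 148.5 − 142.6 = 5.9 | 0.78 | not tabulated |
| 2% | 27.1 | 147.0 − 135.6 = 11.4 | 0.75 | not tabulated |
| 3% | 25.8 | 145.5 − 128.8 = 16.7 | 0.72 | 0.79 |
| 5% | 23.2 | 142.5 − 116.1 = 26.4 | 0.67 | 0.76 |
| 10% | 17.7 | 135.0 − 88.6 = 46.4 | 0.53 | 0.74 |

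The last column comes from 1,500 simulated trials with participant and device effects fitted to every valid session; its standard error is about 1 percentage point.

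**4. A second route.** Here f = 0.2, rho = 0.5, epsilon = 1, and a fixed number of the 30 participants each lack one random session (4,000 simulated trials, error about 0.7 points):

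| Participants incomplete | Valid sessions discarded | Complete sets | All available sessions |
|---|---|---|---|
| 0 | 0 | 0.782 | 0.782 |
| 3 | 12 | 0.722 | 0.771 |
| 6 | 24 | 0.669 | 0.764 |
| 8 | 32 | 0.623 | 0.753 |

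Both routes agree: the complete-set analysis loses much more power than the missing sessions themselves require.

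**5. Sensitivity to correlation.** At rho = 0.6 and epsilon = 1, power is 0.877 with 30 sets and 0.82 with 26, so the study could lose four participants and stay above 0.80.

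**The case against.** **Few sets may be incomplete.** Volunteers are healthy, cold hypersensitivity is an exclusion, adverse reactions are not expected, and visits have no fixed window, so a missed one can be rearranged. This stands as a limit on size. On the calibrated figures, one to three incomplete participants leave power at 0.78 to 0.75. A correlation of 0.6 would absorb a loss of four. It does not supply the missing rule.

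**Ending a session need not lose a set.** A reader might infer that anyone who ends a session drops out of every five-device comparison. The documents do not support that. The Ethical issues section offers a repeat for mitigable causes, and an early-ended session keeps its 5-minute readings, so comparisons at earlier time points could stay complete. The loss applies measure by measure and is certain only for a session that is wholly missing and not made up.

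**Selection.** A reader might also infer that complete sets bias the device comparison, because people who become very cold stop, and that a mixed model would cure this. Much of that mechanism lies outside this point: an adverse reaction that cannot be mitigated leads to withdrawal of the data, which no analysis can recover. Nor does the remedy work for device differences. In an assumed model (four devices with mean 14°C, one with 10°C, between- and within-person SD both 1.5°C, stopping more likely at colder skin), the true difference is 4.0°C:

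| Stops on the coldest device | Complete sets | Mixed model |
|---|---|---|
| 12% | 3.85°C | 3.81°C |
| 21% | 3.77°C | 3.71°C |

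Stopping depends on the session's own unrecorded temperature, so the data are not missing at random. Only the coldest device's mean improves (10.34 against 10.62°C at 21% stops, true 10.0). With differences that large, power is not in question either: it is 0.97 with five complete sets. The selection argument is therefore no reason for the fix.

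**Conclusion.** The point holds in limited form. The two named tests discard a participant's remaining valid sessions whenever one device has no value for the measure analysed, and the plan has neither a rule for this nor any allowance above 30. This should be changed because the remedy is cheap; it is not a flaw that invalidates the design.

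The size depends on missing rates that the documents do not give. It is about 2 points of power at 1% of sessions missing, 8 at 3%, 13 at 5% and 27 at 10%. At the last three rates, analysing all retained sessions brings the loss down to about 1, 4 and 6 points. These figures assume 0.80 at 30 complete sets, sphericity and sessions missing at random. The loss is smaller if the correlation exceeds 0.5. Participants whose data are withdrawn under the Ethical issues section are outside the conclusion.

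**What to change.** Amend the Analysis section to state that:

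- each continuous temperature measure is analysed with a linear mixed model, device fixed and participant random, using every session from participants whose data are retained;
- the comfort rating is analysed with a cumulative-link mixed model or the Skillings-Mack test in place of Friedman;
- the report gives the number of sessions per participant, and the missing sessions with reasons by device;
- the analysis of complete sets is a sensitivity analysis;
- a session ended early and not repeated has a stated status for each measure.

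The counts and reasons by device are needed because the model does not correct for temperature-related stopping; they let a reader judge whether it occurred.

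**Cost.** Wording, slightly more analysis work and reliance on model assumptions. Standard software suffices, with no extra participants or visits. With no sessions missing, the mixed model gives essentially the planned ANOVA result.

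**Alternative.** If the complete-block tests are kept, recruit 30 / (1 − d), where d is the share of participants expected to be incomplete: 32 at 5%, 34 at 10%, 36 at 15% and 38 at 20%. This costs more and still discards valid sessions.

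### After an adverse reaction that cannot be mitigated, the plan withdraws the participant's collected data without any request, and this conflicts with its own instruction to store reactions with those data

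*Combined protocol and SAP*

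**What the plan says.** The Ethical issues section contains two separate routes by which data leave the study.

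- **The participant's choice.** "Participants have the right to withdraw themselves and any collected data from the study at any time during", and for 7 days afterwards.
- **The investigators' rule.** "If a test is terminated due to an adverse reaction that can not be mitigated in future", then "the participant (and any collected data) will be thanked for their time and withdrawn from the study". No request or choice by the participant is mentioned.

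The same section says of adverse reactions: "however any that occur shall be recorded and monitored until things return to baseline/normal". It adds: "Any reported pain (or other adverse reactions) shall be stored along with the data collected for that participant". It does not say whether that record stays when the participant's data are withdrawn, or whether reactions are reported by device.

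A test stopped for a reason that can be mitigated follows a different path: "participants will be offered the opportunity to repeat the test another day, should they wish to continue taking part in the study". Whether the first attempt is then kept is not stated.

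On comfort, the Protocol section says: "After each test, participants will also be asked to respond to the following question using a 5-point Likert scale". The stated purpose is to learn about differences in perception that may bear on patients' adherence. Whether the question is asked after a terminated test is not stated.

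The Analysis section plans a repeated measures ANOVA, or a Friedman test for non-normal data. It has no rule for terminated tests or withdrawn participants, and no reporting of adverse reactions.

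**The concern.** A participant's right to remove their own data needs no defence. The second route is different: it takes the data out because a device was not tolerated, whether or not the participant wants that. Removal therefore depends on tolerability, and someone who had to stop because of a device is highly informative about whether patients would keep using it.

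Three things are at stake:

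- The participant's valid sessions on other devices go as well as the stopped one.
- Any temperature readings and any comfort rating from the stopped test go too.
- The storage and withdrawal sentences cannot both be followed without a further rule. If the reaction record is held with the participant's data and those data are withdrawn, the text leaves open whether the reaction is still counted.

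**Working it through.** **Inputs from the documents.** There are 30 participants and 5 devices, each participant uses every device, and the order is random (Design). The documents give no termination rate, no between-device correlation and no comfort distribution, so those are assumptions below. The plan states no figure on this point.

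**1. Valid sessions removed.** Under random order, the responsible device is equally likely to fall in positions 1 to 5, so 0, 1, 2, 3 or 4 sessions precede it. Mean = (0+1+2+3+4)/5 = 2.

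**2. Shift in a two-device contrast, 1 of 30 removed.** Assume normal outcomes with SD 1 and removal of the most extreme 1/30. The cut is z = 1.834, with density 0.0742. The mean of those remaining moves by 0.0742/(29/30) = 0.077 SD.

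- *Stopping depends on the response to one device.* Shift = 0.077 × (1 − ρ).
- *Stopping depends on the within-person difference between devices.* That difference has SD √(2(1 − ρ)), so shift = 0.077 × √(2(1 − ρ)).
- *Standard error of the paired contrast.* √(2(1 − ρ)/30).

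| Assumed ρ | Shift, one device's response | Shift, device difference | Standard error |
|---|---|---|---|
| 0.3 | 0.054 | 0.091 | 0.216 |
| 0.5 | 0.038 | 0.077 | 0.183 |
| 0.7 | 0.023 | 0.059 | 0.141 |

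At ρ = 0.5 the shift is 0.038/0.183 = 0.21 or 0.077/0.183 = 0.42 of a standard error. If stopping correlates only 0.3 to 0.5 with the response to one device, 0.038 becomes 0.012 to 0.019 SD.

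**3. Comfort scale.** Code 1 as very comfortable and 5 as very uncomfortable. Suppose one stopped participant rates the device 5 and the other 29 average 2.5. The full mean is (5 + 29 × 2.5)/30 = 2.58; after removal it is 2.50, a shift of 0.08 points. With 3 of 30 stopped, a rate the documents do not support, the shift is 2.75 − 2.50 = 0.25. Both figures assume the rating is collected after the stop.

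**4. Count of terminations.** If the reaction record is withdrawn too, 1 of 30 (3.3%, exact 95% CI 0.1% to 17.2%) becomes 0 of 29, with upper limit 1 − 0.025^(1/29) = 11.9%. If the record is kept, this distortion does not arise.

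**5. Does retention help?** A comfort simulation used 400,000 participants, 5 devices in random order, latent correlation 0.5, ratings 1 to 5 at an assumed 20/35/25/15/5%, no true difference, the worst responses on one device stopped at 1 in 30, and later sessions not run. The shift for that device against the rest was:

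| Handling | Shift (points) |
|---|---|
| Data deleted, or complete sets only | −0.043 |
| Retained, comfort asked after the stop | 0.001 |
| Retained, comfort not asked after the stop | −0.049 |

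A temperature simulation (200,000 participants, six 5-minute readings; assumed variance shares 0.50 participant, 0.35 participant-by-device, 0.15 residual) gave these shifts in the 30-minute contrast at 1 in 30: 0.03 SD with deletion, 0.005 to 0.008 SD with a mixed model using readings up to the stop, and 0.034 to 0.036 SD with a mixed model using none from the stopped session. The Monte Carlo standard error was about 0.002 in both.

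**The case against.** The strongest reply is that the clause changes little by itself. A repeated measures ANOVA or Friedman test on complete sets would normally drop the same participants even if their data were kept. The simulation agrees: without a rating after the stop, retention leaves the comfort shift where it was. **This stands.** A reader might infer that the clause biases the planned device comparisons; the documents do not support that. The clause prevents any other analysis or by-device table from using the data, and the current plan contains none.

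Second, the trigger is narrow. Participants are healthy volunteers with cold contraindications excluded, and "Adverse reactions (e.g. pain) to the testing protocol are not expected due to the low-risk nature of the study". **This also stands**, and it limits the size. A reader might infer that pain above 5/10 is enough to remove data. It is not: that stops the test, and only an adverse reaction that cannot be mitigated leads to withdrawal.

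Third, a reader might infer that evidence of harm is destroyed. The text says withdrawn, not destroyed, and separately orders reactions to be recorded and stored. Equally, the rating on the stopped device may never be collected, in which case the clause cannot remove it. What can be said is that earlier sessions are removed, that anything collected in the stopped test is removed, and that the fate of the reaction record is unclear. The 0 of 29 example needs the least favourable reading.

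None of this answers the conflict between the storage and withdrawal sentences, or supplies a reason to remove data that the participant has not asked to have removed.

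**Conclusion.** The point holds, at minor severity. A stated rule removes data according to tolerability, without a request, and conflicts with the instruction to store reactions with that participant's data.

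The numerical effect is zero if no test is stopped. With 1 of 30 removed it is about 0.04 SD if stopping follows the response to one device, or about 0.08 SD if it follows the difference between devices, against a standard error of 0.18 SD. These figures rest on an assumed correlation of 0.5, normal outcomes and removal of the most extreme response. They are illustrations, not bounds. The descriptive loss matters more: tolerability information by device may be missing, and on the least favourable reading a termination goes uncounted.

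**What to change.** Leave the rules for stopping a test and for withdrawing a participant from further testing unchanged.

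1. Replace the data clause with: *data collected up to termination are retained and analysed unless the participant asks for their removal.* Reconcile it with the sentence on storing reactions, so that the fate of the reaction record is explicit.
2. State that the comfort question is also asked after a terminated test.
3. Report terminations, adverse reactions and comfort ratings by device over all started tests, including first attempts later repeated.

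Optional additions are a comfort analysis that accepts incomplete sets, such as an ordinal mixed model, and a temperature sensitivity analysis using readings up to the stop. The first helps only if step 2 is done; the second helps only as far as early readings predict later ones. A mixed model that treats the whole stopped session as missing should not be relied on, since it did no better than deletion in the simulation.

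The cost is a few sentences of wording, a check that the consent text (not available here) agrees with retention, and a little more analysis work. No extra participants or instruments are needed. If testing is already complete, step 3 remains possible wherever records were kept.

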All eligible participants will first be required to provide informed consent prior to their participation in the study. Once this has been obtained, participants will each attend 5 individual testing sessions, each lasting no longer than 60 minutes. The height and mass of the participants will be measured during the first testing session in order to calculate BMI, and participants' age and sex will be recorded and included in the later data analysis.

Participants will be required to remain in a seated position with their leg in full extension and elevated, parallel to the floor, for the duration of each test. The leg that will be used for the study will be randomly selected for each participant, and will remain the same for each condition. Skin temperature will be measured using a thermocouple, which will be attached with tape 20 mm distal to the patella. One of the cryocompression devices (Physiolab S1; Physiolab ice pack; GameReady; Cryo/Cuff; or VPulse) will then be attached to the leg of the participant and the test will begin. Depending on the condition to which a participant has been randomly assigned for a given test, a different device will be used. The temperature and pressure settings for each test will be set according to the manufacturers' recommendations which vary between devices. The lowest temperature setting that will be used throughout the study will be 1°C (GameReady device) and the highest pressure setting that will be used is 50 mmHg (GameReady and Physiolab S1 devices). None of the temperature or pressure settings used are deemed to be unsafe or have a high risk of adverse reactions, as long as participants are not contraindicated according to the abovementioned exclusion criteria.

The temperature of the skin will be measured using a k-type thermocouple attached to an infrared thermometer immediately prior to the application of a device, and then every 5 minutes for the duration of the test. The length of a test will be 30 minutes, in accordance with the manufacturers' instructions/recommendations for each device.

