[name] (JB) receives payment from Physiolab Technologies Ltd as an external research consultant. Physiolab Technologies Ltd have had no influence on the design of the study. Although the study is being led by JB, who will proceed in his role impartially, the co-authors of this research will assist with the data collection, analysis, and eventual manuscript preparation to ensure that any unethical investigator biases are avoided. In addition to the consultancy fees for JB, Physiolab Technologies Ltd will provide the equipment to be used in this study. The other authors of this work have no conflict of interest to declare.

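### The study lead is a paid consultant to the company named on two of the five devices and no masked analysis is described; coded labels and a locked analysis would reduce the risk of bias cheaply

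*Combined protocol and SAP*

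**What the plan says.** The Conflict of interest declaration states that the lead investigator "receives payment from Physiolab Technologies Ltd as an external research consultant" and that "Physiolab Technologies Ltd will provide the equipment to be used in this study". Methods, Protocol lists the devices as "Physiolab S1; Physiolab ice pack; GameReady; Cryo/Cuff; or VPulse", so two of the five bear that company's name.

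The same declaration gives the safeguards. The lead is to act impartially, the company is said not to have influenced the design, and the other authors declare no conflict. To prevent investigator bias, "the co-authors of this research will assist with the data collection, analysis, and eventual manuscript preparation".

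Methods, Protocol lists five kinds of measure: skin temperature at each time point, minimum temperature, time to that minimum, time within 10-15°C, and a comfort rating. None is named as primary. The Analysis section sets a Kolmogorov-Smirnov test first, then repeated measures analysis of variance for normal data; "A Friedman test will be performed on any data that are not normally distributed".

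Under Ethical issues, "If a test is terminated for a reason that could be mitigated in future", the participant is offered a repeat. If the cause is an adverse reaction that cannot be mitigated, the participant and the data already collected are withdrawn.

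**The concern.** The declaration accepts that investigator bias is a risk and includes analysis among the activities to be protected. The protection offered is help from colleagues. Someone who assists does not necessarily decide, and the plan does not say that the lead steps back from any analytic decision. Nor does it say that whoever decides will be unaware of which device produced which numbers.

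Device use cannot be hidden from participants or session staff, but the labels in the analysis data set can be. If choices are made with device names in view, they could favour one company's products without anyone intending it. A reader of a result favourable to a Physiolab device could not rule this out, because disclosure reports the interest without controlling its effect.

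**Working it through.** No calculation settles this point. The check sets the sections side by side.

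**Step 1: the interest.** The payment and the equipment supply are stated in the Conflict of interest declaration. The device names are in Methods, Protocol. That the company makes both Physiolab devices follows only from the shared name.

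**Step 2: masking.** No section mentions blinding, coded labels or an independent analyst. The absence of masking is therefore read from silence; the plan does not state that the analysis is open.

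**Step 3: what is open, and what coding can reach.**

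| Decision | What the plan fixes | What it leaves open | Reached by coded labels? |
|---|---|---|---|
| Measure to emphasise | Five kinds of measure are recorded | Which is primary | Yes, if settled before the code is opened |
| Post-hoc comparisons | Change from baseline and differences between groups will be examined | Which device pairs, and any adjustment | Yes |
| ANOVA or Friedman | A rule based on a normality test | The threshold; raw data or residuals; by device or pooled | Yes, but discretion is limited |
| Exclusions at analysis | Participants' right to withdraw data; withdrawal after a non-mitigable adverse reaction | Incomplete sets of sessions, doubtful readings | Yes |
| Terminated test: mitigable or not | Repeat, or withdrawal with data | The criterion and who decides | No; the device is in view |
| Device application and comfort rating | Manufacturers' instructions; a 5-point scale | Not an analysis choice | No |

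**Step 4: what one termination decision can do.** Each participant uses all five devices. Read plainly, a withdrawal with all collected data removes one of 30 participants (1/30 = 3.3%), and up to five sessions, from every comparison. A repeat keeps them all. So the classification matters even if terminations are rare.

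**Step 5: effect of the remedy on the plan's own figure.** The plan states N = 30 for power 0.8, alpha 0.05 and f = 0.2. It gives neither the within-participant correlation nor the sphericity correction. Assuming 0.5 and 1, the noncentrality is N·m·f²/(1−ρ) = 30 × 5 × 0.04/0.5 = 12, on 4 and 116 degrees of freedom. Power is then 0.784, and 32 participants are needed for 0.80, which is close to the stated figure. Device labels do not enter this formula, so coding them changes neither N, alpha nor power.

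**The case against.** The strongest case against is that the plan contains no error here. The conflict is disclosed, the other authors declare none, and the company is said to have had no part in the design. Four of the five kinds of measure are thermocouple readings or derive from them, which narrows discretion. The choice between ANOVA and Friedman follows a rule. Naming a primary outcome would deal with selective emphasis more directly than coding would. All of this is fair, and it makes the point a recommendation for a cheap safeguard. It does not dispose of it: a primary outcome would not settle exclusions or comparisons, and none of the stated safeguards keeps device identity from whoever makes those decisions.

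A reader might infer stronger claims that the documents do not support:

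- **That coding would remove the bias.** Co-authors help with both data collection and analysis, so an analyst may have run the sessions. A device may also be recognised from its temperatures; GameReady has the lowest setting, 1°C.
- **That false-positive rates over several measures or device pairs give the size of the problem.** Those rates are the same whether devices are named or lettered. An omnibus test has no direction. Of the 5 × 4/2 = 10 pairs, only 2 × 3 = 6 set a Physiolab device against a competitor; one is Physiolab against Physiolab and three are between competitors.
- **That the company sponsors the trial.** The declaration mentions consultancy fees and equipment only.

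**Conclusion.** The point holds as a gap in safeguards. The lead has a financial tie to the company named on two of the five devices. Beyond assurances, the only analysis-stage protection is that unconflicted co-authors assist, and several decisions that could affect the comparison are unspecified. Nothing in the documents shows that any decision was, or will be, made improperly.

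The size of any bias cannot be computed from the documents, and no figure should be attached to it.

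The conclusion rests on two readings: that silence about masking means none is planned, and that the shared name means the company makes both devices. If a masked analysis is planned but not written down, stating it would answer most of the point. The change is worth making because it serves the declaration's own aim at little cost.

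**What to change.** Add to the Analysis section and the Conflict of interest declaration:

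1. A co-author without the company tie replaces the device names with codes A to E in the analysis data set and holds the key.
2. An unconflicted co-author, where possible one who did not run the sessions, decides the primary measure, the form of the normality check and resulting test, the device comparisons and the data exclusions. That person runs the primary analysis on the coded data. The decisions and analysis are dated and locked before the code is opened.
3. Separately, because a live session cannot be masked, an unconflicted co-author classifies each terminated test as mitigable or not and records the reason. This leaves the clinical rule for stopping a test unchanged.

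The cost is one coding step, a dated lock and a short log of terminations, all done by co-authors already named to help. No participants, visits or equipment are added. The drawback is that masking will be partial, for the reasons given above. Device application and comfort ratings stay unmasked, and the report should say so.
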